5.2 Handling of Withdrawals and Drop-outs

For the analysis of the primary safety endpoint, 22 patients are required. If withdrawals and drop-outs occur after the implantation of the ARGOS-IO, a recalculation of the critical value for the decision rule of Simon's Design is necessary. The recalculation will be performed based on the method described by Simon (Simon, 1989).

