9.3 Level of significance and the power of the clinical investigation

Significance level is set to 0.05, Power to 80%.

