9.4 Expected drop-out rates

This section is not applicable.

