2.6 Handling of Screening Failures and Drop-outs

Screen failures are patients who have signed the informed consent form but fail to meet eligibility criteria for enrolment, e.g., they do not meet one or more of the inclusion criteria or do meet one or more of the exclusion criteria. Such patients will be replaced.

Patients will be informed that they have the right to withdraw from the study at any time. The investigator must determine whether voluntary withdrawal is due to safety concerns. All patients who withdraw from the study after implantation and before completing the follow-up visits per protocol will be considered as drop-outs. Patients who drop out or are withdrawn after implantation will not be replaced.

Reasons for withdrawal are:

- The patient withdraws informed consent,
- it is determined during surgery that the patient is not feasible for ARGOS-IO pressure sensor implantation,
- the ARGOS-IO pressure sensor must be removed or replaced for any reason,
- patient becomes pregnant between screening and surgery.

Unless the patient revokes his/her permission to use it, any data collected up to the point of the patient's withdrawal will be included in the safety analysis. The data of all patients who undergo implantation of the ARGOS-IO pressure sensor will be included in the efficacy analysis under the Full Analysis Set.

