2.9 Sample Size Calculation

The primary aim of this study is to show “safety”, which will be evaluated based on the percentage of subjects who experience an SADE (= “non-safety), as defined in the primary endpoints.. To minimize the required sample size and consequently the number of patients exposed to risk while at the same time maximizing the chances of detecting safety events, the sample size calculation follows the principle of a two-stage design as proposed by Simon (Simon, 1989). The event of interest was defined as patients with at least one serious device related adverse event (SADE) in the 3 month period immediately following implantation. Based on a probability of non-events of $p_0=0.75$ for the first stage and an overall acceptable probability of $p_1=0.94$, a sample size of at least 11 evaluable patients in the first stage and additional 11 patients in the second stage are required. This maintains a type 1 error probability of 5% and the power of 80% based on minimizing the maximal sample size. Table 2 summarizes the consequences of the sample size calculation on the study design.

Table 2: Two-stage study design

	First Stage	Overall
SADE-free Patients		
Proportion	$p_0 = 0.75$	$p_1 = 0.94$
Minimum number required	10	20
Patients with SADE		
Proportion	$1 - p_0 = 0.25$	$1 - p_1 = 0.06$
Maximum number allowed	1	2
Total Number of Patients	11	22

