7.2 Evaluation of Primary Safety Variables

Incidence of SADEs in the 3 month period immediately following implantation will be assessed. The decision on safety follows the rule of Simon's optimal two-stage design (parameters: $\alpha=0.05$, $\beta=0.20$, $p_0 = 0.75$, $p_1 = 0.94$). A corresponding 95% confidence interval will be given for the portion of SADEs within the safety population. The confidence interval for the SADE rate will be calculated using the method proposed by Koyama (Koyama & Chen, 2008). These calculations will be based on the number of patients experiencing a SADE based on the safety population. If the obtained confidence interval does not include any value lower than 0.94, it can be concluded that the SADE rate is at most 6%.

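### SAP 5.2 recalculates the Simon limit after any post-implantation withdrawal, even one after the 3-month endpoint is known; taking one such patient out of n lowers the limit from 2 of 22 to 1 of 21

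*SAP*

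**What the plan says.** **Endpoint.** SAP 6.2 counts patients with an SADE within 3 months of implantation. SAP 2.1 and 2.10 end the trial if more than 1 of the first 11 patients has an SADE. SAP 2.1 concludes safety if no more than 2 of 22 do.

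**Trigger.** SAP 5.2 says that 22 patients are needed for the primary safety endpoint, and continues: "If withdrawals and drop-outs occur after the implantation of the ARGOS-IO, a recalculation of the critical value for the decision rule" is then needed, by Simon's method. It gives no time limit, no n and no alpha to be held.

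**Who counts as a drop-out.** SAP 2.6: "All patients who withdraw from the study after implantation and before completing the follow-up visits per protocol will be considered as drop-outs". Those visits run to day 360 (SAP 2.3). One listed reason for withdrawal is that "the ARGOS-IO pressure sensor must be removed or replaced for any reason". Nobody is replaced after implantation.

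**Text pointing the other way.** SAP 2.6 keeps data up to withdrawal in the safety analysis unless the patient revokes permission. SAP 4.1 defines the safety population as all attempted implantations. SAP 5.1 uses observed data as they stand. SAP 7.2 bases the primary analysis on the safety population.

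**Error rates.** SAP 2.9, on the 11 + 11 design: "This maintains a type 1 error probability of 5% and the power of 80% based on minimizing the maximal sample size". Protocol 9.3 repeats the 5% level and 80% power. Protocol 9.4, on expected drop-out: "This section is not applicable".

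**The concern.** The trigger for changing the pass/fail limit is tied to 12 months of follow-up, but the endpoint it governs is settled at 3 months. A patient who leaves at month 8 with a known 3-month outcome sets off SAP 5.2 as written. So does a patient whose sensor is removed after an SADE, although that outcome is also known.

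Recalculating a critical value makes sense only if n has changed, so the natural implication of SAP 5.2 is that the leaver comes out of the 22. Other sections of the SAP support keeping that patient in. The plan does not settle the conflict, and it concerns the only hypothesis test in the study (SAP 5.3). The trial is open-label, so the choice of n could be made with the SADE count already known.

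The design also has no room for loss. Its power is barely 80% at exactly 22 patients, and no drop-out was planned for.

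**Working it through.** **Inputs.** SADE rate 0.25 under the null and 0.06 under the alternative (SAP 7.2: "parameters: $\alpha=0.05$, $\beta=0.20$, $p_0 = 0.75$, $p_1 = 0.94", as SADE-free proportions). Stage sizes 11 and 11, limits 1 of 11 and 2 of 22 (SAP 2.9, Table 2).

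**Formula.** Let X1 be the SADE count in stage 1 and X2 the count in stage 2, both binomial with SADE rate q. With final limit 2:

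P(pass) = P(X1=0) × P(X2≤2) + P(X1=1) × P(X2≤1)

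With final limit 1, replace the two X2 bounds by 1 and 0. Alpha is P(pass) at q = 0.25; power is P(pass) at q = 0.06.

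**Step 1: reproduce the plan (2 of 22).**

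- For 11 patients at q = 0.25, the probabilities of 0, 1 and 2 SADEs are 0.0422, 0.1549 and 0.2581. Alpha = 0.0422 × 0.4552 + 0.1549 × 0.1971 = 0.0497.
- At q = 0.06 they are 0.5063, 0.3555 and 0.1135. Power = 0.5063 × 0.9753 + 0.3555 × 0.8618 = 0.800 (0.8001 unrounded).

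The stated 5% and 80% are reproduced. A full search over stage sizes and limits finds no two-stage design with fewer than 22 patients that meets both.

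**Step 2: take one stage 2 patient out (n = 21, second stage of 10).**

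- For 10 patients at q = 0.25, the probabilities of 0, 1 and 2 SADEs are 0.0563, 0.1877 and 0.2816.
- Limit 2: alpha = 0.0422 × 0.5256 + 0.1549 × 0.2440 = 0.060, above 0.05.
- Limit 1: alpha = 0.0422 × 0.2440 + 0.1549 × 0.0563 = 0.019.
- At q = 0.06, 10 patients have 0 or 1 SADE with probabilities 0.5386 and 0.3438. Power with limit 1 = 0.5063 × 0.8824 + 0.3555 × 0.5386 = 0.638.

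Holding alpha at 0.05 therefore forces the limit from 2 to 1. If a stage 1 patient is removed instead, limit 2 gives alpha 0.0626 and limit 1 again gives 0.019 and 0.638.

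**Step 3: limits at smaller n (stage 1 kept at 1 of 11, alpha ≤ 0.05).**

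| n | final limit | alpha | power |
|---|---|---|---|
| 22 | 2 | 0.0497 | 0.800 |
| 21 | 1 | 0.019 | 0.638 |
| 20 | 1 | 0.024 | 0.660 |
| 19 | 1 | 0.031 | 0.683 |
| 18 | 1 | 0.039 | 0.706 |
| 17 | 0 | 0.008 | 0.349 |

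At n = 17, limit 1 gives alpha 0.0501 and just misses.

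**Step 4: results that would change.** A pass with exactly 2 SADEs needs 0 in stage 1 and 2 in stage 2, or 1 in each. At q = 0.06 the probability is 0.5063 × 0.1135 + 0.3555² = 0.184. As a share of all passes it is 0.184 / 0.800 = 23%. If an SADE-free late leaver is then removed, 2 SADEs remain against a limit of 1, and the pass becomes a failure.

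**The case against.** **The text does not order removal.** SAP 5.2 names no n. It opens by tying the 22 patients to the primary safety endpoint, SAP 2.9 speaks of evaluable patients, and SAP 2.6, 4.1, 5.1 and 7.2 would keep a month-8 leaver among the 22. Recalculating at n = 22 returns the limit of 2. This stands: a reader might infer that SAP 5.2 explicitly drops late leavers, and it does not. What remains is a stated trigger with no time limit, whose literal implication conflicts with those sections.

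**Explanted patients.** A reader might infer that an SADE leading to sensor removal is either lost with the patient or penalised twice. The documents do not support this. The event stays in the safety population unless permission to use the data is revoked, and no section takes that patient out of the denominator.

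**Power.** Any minimal exact design loses its nominal properties when n falls, and SAP 5.2 itself says 22 are needed. SAP 8.2 also reports an interim analysis after all subjects completed Visit 9 (6 months). If that means every implanted patient, no 3-month status is unknown, and under a properly limited rule the limit stays at 2. That reduces the practical loss of power but does not answer the problem of withdrawals after that visit.

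**Conclusion.** The concern holds as a conflict within the SAP that can reverse the primary result. One late withdrawal, if taken out of n, lowers the limit from 2 of 22 to 1 of 21 and would fail a trial with exactly 2 SADEs, a pass that has probability 0.18 at a true 6% rate.

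This rests on four conditions: the leaver is removed from n, the leaver had no SADE, the stage 1 rule stays at 1 of 11, and alpha is held at 0.05.

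Three stronger figures should not be inferred:

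- The unconditional chance of exactly 2 SADEs in 22 is 0.241. It includes 0.1135 × 0.5063 = 0.057 for trials with both events in stage 1, which stop anyway. The relevant figure is 0.184, and it is not the chance of a reversal, because a late withdrawal must also occur.
- The 64% power is not a flat consequence of losing one patient. With stage 1 redesigned, the best power at n = 21 is 0.755, still below 80%. With limit 2 kept, power is 0.810 but alpha is 0.060.
- No drop-out rate is documented. At an assumed 2%, 5% or 10% per patient, the chance of at least one loss among 22 is 36%, 68% or 90% (1 − 0.98^22, 1 − 0.95^22, 1 − 0.90^22). These figures do not separate losses before and after 3 months, so they do not measure the defect.

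**What to change.** Rewrite SAP 5.2 along these lines:

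- A patient is evaluable if an SADE occurred within 3 months or if safety status at 3 months (V07) is known, whatever happens later.
- Patients withdrawn after an SADE stay in both the count and the denominator.
- The critical value is recalculated only for patients without an SADE whose 3-month status is unknown. In that case n is the number of evaluable patients, the stage 1 rule stays at 1 of 11, and alpha is at most 0.05.
- The limits are fixed in advance: 2 SADEs at n = 22, 1 at n = 18 to 21, 0 at n = 17.

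In Protocol 9.3 and SAP 2.9, state that 80% power holds only with 22 evaluable patients and is about 64% at 21 under this recalculation rule.

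The cost is SAP wording and a less favourable power statement. No extra patients are needed.

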5.3 Handling of Multiple Comparisons and Multiple Primary Variables

A statistical test will be only performed for the primary safety variable. The primary performance variable is not evaluated by using a statistical test but analysed by descriptive and explorative statistical methods. None of the other variables will be tested in a deductive sense. Thus, no multiple testing problems may evolve.

5.4 Data Review

A data safety monitoring board (DSMB) will be established prior to enrolment of the first patient. The DSMB is to review the safety data, including SAEs/SADEs, on a regular basis or if a SADE occurs, and will advise on any changes required in the conduct this clinical investigation. The DSMB will also review the data of the interim analysis and give recommendations to the Sponsor to either continue the clinical investigation (with or without an amendment of the clinical investigation plan) or to stop enrolment into the clinical investigation based on safety concerns.

The first meeting is planned when the 11 patients in the first stage have completed their 3 month follow-up visits. Enrollment will be halted to allow the DSMB to review their data and for changes to be made to the clinical investigation plan, if recommended. The DSMB may hold additional meetings whenever deemed appropriate.

6. Variables for Analysis

6.1 Demographics and Baseline Characteristics

The following assessments shall be performed at Visit 0 and analysed as baseline values:

- Demographic and baseline characteristics including year of birth, sex, race, weight, height, child-bearing potential, educational level,, and source of patient referral
- Previous and concomitant medications
- Medical history and glaucoma medical history including length of time since diagnosis of glaucoma and anti-glaucoma medication
- Ophthalmic examinations including
 - visual acuity measurements
 - anterior segment measurements
 - posterior segment measurements

- anterior segment abnormalities
- posterior segment abnormalities
- intraocular pressure using Goldmann Applanation Tonometry (GAT)
- other examinations (e.g optical biometry)

6.2 Primary Safety Variables

For the assessment of the primary safety endpoint, the number of patients who experienced a SADE within the 3 months following implantation is examined. A SADE is defined as any adverse event that both

- is considered by the Investigator to have a possible, probable or definite relationship to the device and
- that meets any of the following criteria of a serious adverse event:
 - resulted in death, permanent damage or disability or a congenital anomaly,
 - was life threatening,
 - required hospitalization or intervention to prevent permanent impairment or damage.

6.3 Primary Performance Variables

To evaluate the performance of the ARGOS-IO system compared to GAT from day 30 through day 180, limits of agreement between IOP measurements made using GAT and measurements made using the ARGOS-IO system will be examined from V05 (day 30) through V09 (day 180).

6.4 Secondary Safety Variables

Evaluation of the secondary safety objectives include the assessment of the incidence, nature, seriousness, severity and duration of both adverse events and adverse device effects in the 3, 6 and 12 months immediately following implantation of the ARGOS-IO pressure sensor.

6.5 Secondary Performance Variables

Assessment of the secondary performance variables include

- Limits of agreement between IOP measurements made using GAT and the ARGOS-IO system from Visit 10 through Visit 11
- Incidence of observed of device malfunctions in the 3, 6 and 12 months following implantation
- User acceptance of the implantation procedure by means of evaluation of the implantation procedure questionnaires (investigators)
- User acceptance of the ARGOS-IO system at the investigational site by means of evaluation of the investigator acceptance questionnaires (investigators)
- User acceptance of the ARGOS-IO system at home by means of evaluation of patient acceptance questionnaires (patients) at Visit 11
- Daily IOP self-measurement profiles (patients).

6.6 Other Variables

Other assessed variables are:

- Surgery and lens transplantation variables
- Variables regarding complications during surgery
- Ophthalmic examinations at the follow-up visits including
 - visual acuity and visual field measurements
 - anterior segment measurements
 - posterior segment measurements
 - anterior segment abnormalities
 - posterior segment abnormalities

7. Statistical Analysis Methods

7.1 Evaluation of Demographics and Baseline Characteristics

7.1.1 Disposition of Patients

The number and percentage of screened, enrolled and implanted patients, as well as those who complete the follow-up will be tabulated for the safety population and FAS. The number and percentage of screen failures and early withdrawals will also be tabulated, along with the reason for the screen failure or drop-out.

7.1.2 Demographics

Demographic data and baseline characteristics listed in section 6.1 will be presented using standard descriptive statistics, i.e. summaries (n, mean, standard deviation, median, minimum and maximum) for quantitative variables and absolute as well as percent frequencies (n, %) for qualitative (i.e. categorical data). The analysis is based on the FAS.

7.1.3 Medical History, Concomitant Diseases, Previous and Concomitant Medication

Glaucoma related medical history will be assessed separated from medical history. The time since diagnosis of glaucoma will be displayed in days using statistical summaries (n, mean, standard deviation, median, minimum and maximum). The duration will be calculated as follows:

$$\text{Time since diagnosis} = \text{Date of surgery (V01)} - \text{Date of diagnosis} + 1$$

Absolute and relative frequencies (n, %) of subjects will be used for presenting the type of glaucoma and other related questions with categorical response options.

Medical history and concomitant diseases not related to glaucoma will be described based on MedDRA system organ class and preferred term levels. Absolute and relative frequencies (n, %) of subjects will be provided.

Absolute and relative frequencies (n %) of subjects with previous and concomitant medications will be given based on different Anatomical Therapeutic Chemical Classification [ATC] code levels. Absolute and relative frequencies (n %) will be given. Medical history, concomitant diseases as well as previous and concomitant medication will be presented based on the FAS.

7.2 Evaluation of Primary Safety Variables

Incidence of SADEs in the 3 month period immediately following implantation will be assessed. The decision on safety follows the rule of Simon's optimal two-stage design (parameters: $\alpha=0.05$, $\beta=0.20$, $p_0 = 0.75$, $p_1 = 0.94$). A corresponding 95% confidence interval will be given for the portion of SADEs within the safety population. The confidence interval for the SADE rate will be calculated using the method proposed by Koyama (Koyama & Chen, 2008). These calculations will be based on the number of patients experiencing a SADE based on the safety population. If the obtained confidence interval does not include any value lower than 0.94, it can be concluded that the SADE rate is at most 6%.

7.3 Evaluation of Primary Performance Variables

The primary performance objective is the assessment of the agreement between measurements made using GAT and the ARGOS-IO system from V05 (day 30) through V09 (day 180). If multiple ARGOS-IO system measurements have been made at time points for which paired GAT/ARGOS-IO system measurements are to be compared, the mean of the replicate ARGOS-IO system measurements will be used for agreement evaluation. The agreement evaluation is based on the assumption, that the measurements are constant over the measurement period.

The Bland-Altman method, which compares the mean of paired measurements to their difference will be used to determine the upper and lower limits of agreement expected to contain 95% of the IOP value pairs obtained with the ARGOS-IO system and GAT. The two-sided 95% confidence intervals for each of these limits will be calculated using the Mover method (Zou, 2011) to account for repeated measurements. IOP values will be displayed as Bland-Altman plots of individual measurement pairs by measurement technique for each individual participant as well as mean plots over time (per visit and overall). This analysis is based on the FAS and is repeated for each subgroup as described in section 4.2.

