8.4.4.15 Intraocular pressure (IOP) measurement

Intraocular pressure (IOP) will be measured using two techniques. Goldmann Applanation Tonometry (GAT) will be performed in the clinic at every visit. Beginning at V05, IOP measurement will also be performed with the ARGOS-IO system, both by site personnel at clinic visits and by the patient at home between visits. Only GAT will be used to guide any treatment decisions. The GAT must be performed by preferably one or at maximum two dedicated investigators at each site to reduce potential bias.

IOP measurement in the clinic

Each IOP measurement will be conducted as a series of 1x GAT followed by 3x ARGOS-IO system, except for Visits SC through V04 when only GAT will be used. When series of measurements are made, the GAT must always be used first to avoid operator bias. There should be no more than 10 minutes between the GAT measurement and the first of the ARGOS-IO system measurements in a series, and at least 60 minutes will lie between the last measurement with the ARGOS-IO system in one series and the GAT of the next.

IOP will be measured at least two times at every visit, preferably at the beginning and end of the visit. At Visits 05, 07, 09 and 11, IOP will be measured 4 times. Again, effort should be made to ensure there are at least 60 minutes between measurement series.

ARGOS-IO system measurement by the patient at home

At V05 (D30), after detailed instruction in their use, the patients will receive an individual Mesograph reading device and the Multiline Connector to perform self-tonometry at home. The patients will be requested to perform at least 4 IOP measurements with the Mesograph daily, evenly spread throughout the day. They will also be requested to connect the reader to the Multiline Connector on a regular basis to transfer the recorded IOP data directly into the secure database. No manual recording of data by the patient will be required.

Patients shall be instructed to bring the Mesograph reading device to every visit to permit site staff to check its functionality and to delete the measured IOP data from the device. The device routinely stores up to 3.000 measurements.

 Implandata Ophthalmic Products GmbH	Clinical Investigation Plan ARGOS-02	Revision C <hr/> Page 75 of 106
--	---	------------------------------------

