7.5.1 Limits of Agreement

Limits of agreement between IOP measurements made using GAT and the ARGOS-IO system from V10 (day 240) through V11 (day 360) will be assessed. If multiple ARGOS-IO system measurements have been made at time points for which paired GAT/ARGOS-IO system measurements are to be compared, the mean of the replicate ARGOS-IO system measurements will be used for agreement evaluation. The agreement evaluation is based on the assumption, that the measurements are constant over the measurement period.

The Bland-Altman method will be used to determine the upper and lower limits of agreement expected to contain 95% of the IOP value pairs obtained with the ARGOS-IO system and GAT. The two-sided 95% confidence intervals for each of these limits will be calculated using the Mover method (Zou, 2011) to account for repeated observations. IOP values will be displayed as Bland-Altman plots of individual measurement pairs by measurement technique for each individual participant as well as mean plots over time (per visit and overall).

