8.2 Changes in the Planned Analysis

Departing from the planned analysis, the first DSMB meeting was conducted after 6 patients had completed Visit 4. The sponsor of this trial was enlightened that it is necessary to increase the overall sample size if this first DSMB meeting corresponds to a prepond analysis of the first stage of Simon's two stage design in order to maintain the type I and type II error. The report provided for this DSMB meeting comprised the listings and tables in the DSMB charter plus a table summarizing the compliance of subjects.

The second DSMB meeting was conducted after 11 patients completed Visit 5 (one month after implantation of the medical device). The report provided for this DSMB meeting comprised the listings and tables in the DSMB charter minus the summary of anterior segment examination results, posterior examination results, GAT measurements and ARGOS-IO measurements.

The first interim analysis independent from the DSMB was conducted after 21 subjects completed Visit 5 (one month after implantation of the medical device). The report provided comprised the listings and tables in the DSMB charter plus:

- Summaries of visual field and visual acuity results at screening and follow-up visits
- More detailed information about medical history, concomitant illnesses and previous/concomitant medications
- More detailed information about adverse events
- Additional summaries of GAT measurements and ARGOS-IO measurements including limits of agreement per visit and for all visits

The limits of agreement were provided in a separate document with corresponding table and figures. If multiple ARGOS-IO system measurements have been made at time points for which paired GAT/ARGOS-IO system measurements were to be compared, the mean of the replicate ARGOS-IO system measurements were used for agreement evaluation. Subsequently, this analysis was repeated by using the first replicate ARGOS-IO system measurement instead of the mean of the replicate measurements.

The second interim analysis independent from the DSMB was conducted after all subjects completed Visit 9 (6 months after implantation of the medical device). The report provided comprised the same tables and listings as the report for the interim analysis conducted after 21 subject completed Visit 5.

A. APPENDICES

List of Tables

Table 1	Disposition of patients (SES, FAS)
Table 2	Patient recruitment by month and by site
Table 3	Premature terminations

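### The planned limits of agreement apply to the mean of three ARGOS readings; the final plan has no companion limits for a single reading, which would probably be somewhat wider

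*SAP*

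**What the plan says.** Protocol 8.4.4.15 sets the clinic procedure: "Each IOP measurement will be conducted as a series of 1x GAT followed by 3x ARGOS-IO system". Up to and including V04 only GAT is used.

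SAP 7.3 reduces each series to one pair, with the ARGOS member averaged: "the mean of the replicate ARGOS-IO system measurements will be used for agreement evaluation". It describes the result as the "upper and lower limits of agreement expected to contain 95% of the IOP value pairs obtained with the ARGOS-IO system and GAT". SAP 7.5.1 repeats the averaging rule for the later window: "Limits of agreement between IOP measurements made using GAT and the ARGOS-IO system from V10 (day 240) through V11 (day 360) will be assessed". The protocol synopsis gives the same rule under the primary performance endpoint, so the mean is pre-specified. Both SAP sections assume that pressure does not change while a set of readings is taken. They apply the MOVER method to the confidence intervals around the limits.

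At home, patients are asked to "perform at least 4 IOP measurements with the Mesograph daily, evenly spread throughout the day". No triplicate and no averaging is described for these readings. SAP 4.1 and 7.5.6 keep them out of the FAS evaluation.

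SAP 8.2 reports that, after the mean-based limits were produced at the first interim, "this analysis was repeated by using the first replicate ARGOS-IO system measurement instead of the mean of the replicate measurements". The account of the second interim does not name this run. SAP 7.3, 7.5.1 and Tables 25 and 26 in the appendix contain no first-replicate version. The pairs in Table 25 take their meaning from 7.3, so their ARGOS value is also the mean. Individual clinic readings appear only in Listing 26.

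**The concern.** Averaging three readings shrinks whatever part of the ARGOS error is independent from one reading to the next. Limits built on the average therefore describe a steadier quantity than a single reading. The SAP sentence about 95% of value pairs does not itself say that the ARGOS value is an average, so the limits can easily be read as applying to any one ARGOS reading.

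This bears on the trial's own question, which is how well ARGOS measurements agree with GAT. The device is meant for frequent separate readings, yet no planned final analysis describes the agreement of one reading. The data for it are collected, and the analysis has been run once.

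**Working it through.** **Nothing to reproduce.** Neither document gives an expected SD, a width or an acceptance margin for the limits of agreement. The direction can be derived. The size can only be illustrated.

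**Inputs**
- Readings averaged per series: m = 3 (Protocol 8.4.4.15).
- V, the variance of the difference from all other sources (GAT error, and differences between patients and between series). Not given. As a scale, Protocol 3.3.3 puts the imprecision of repeated IOP measurement at ±5 mmHg. Read as 1.96 SD (an assumption), this gives 5/1.96 = 2.55 mmHg, so V = 6.51. The 7 mmHg in the same sentence fits this reading, since 5 × √2 = 7.07.
- s, the SD of the independent within-series error of one ARGOS reading. Not given. As a scale, Protocol 5.1.1.1 reports a bench pressure accuracy of ±1.32 mmHg. This gives s = 1.32/1.96 = 0.67 if it is a 95% range, or s = 1.32 if it is one SD. Accuracy against a reference is not repeatability in the eye, so this only sets a scale.

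**Formulas**
- Half-width for the mean of three: H3 = 1.96 × √(V + s²/3)
- Half-width for one reading: H1 = 1.96 × √(V + s²)
- Narrowing: 1 − H3/H1
- Share of single-reading differences inside the mean-based limits: 2Φ(1.96 × H3/H1) − 1

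Any error shared by the three readings, such as a calibration offset, belongs in V and does not shrink. For any s above zero, H3 is below H1.

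**Numbers**
- s = 0.67: s² = 0.454. H3 = 1.96 × √(6.51 + 0.151) = 5.06. H1 = 1.96 × √(6.51 + 0.454) = 5.17.
- s = 1.32: s² = 1.742. H3 = 1.96 × √(6.51 + 0.581) = 5.22. H1 = 1.96 × √(6.51 + 1.742) = 5.63.

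| s (mmHg) | Mean of three | Single reading | Narrowing | Single readings covered |
|---|---|---|---|---|
| 0.67 | ±5.06 | ±5.17 | 2.2% | 94.5% |
| 1.32 | ±5.22 | ±5.63 | 7.3% | 93.1% |

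**Sensitivity.** With other-source SDs from 1.5 to 5.0 mmHg and s from 0.67 to 2.55 mmHg, the narrowing runs from 0.6% to 29.0%. The ceiling, with no other variance at all, is 1 − 1/√3 = 42%. The upper part of this range has no support in the documents.

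**Simulation check.** There were 22 patients, each with 16 series over V05 to V09 (4 + 2 + 4 + 2 + 4). Limits came from variance components, with 400 runs and a between-patient SD of 1.5 mmHg added to the inputs above. The narrowing was 1.6% at s = 0.67 (±5.87 against ±5.97) and 5.7% at s = 1.32 (±5.99 against ±6.35).

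**Adding the variance back.** Since V + s² = (V + s²/3) + (2/3)s², adding two thirds of the within-series variance to the variance of the mean-based difference gives the single-reading variance. In the simulation at s = 1.32 this gave ±6.35, the same as using the first replicate.

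**The case against.** The strongest reply is that nothing in the plan is wrong on its own terms. The mean is fixed in the protocol synopsis, and the SAP follows it. The endpoint is agreement with GAT at clinic visits, where three ARGOS readings are always taken, and patient readings are expressly outside the evaluation. For the pair that SAP 7.3 defines, the 95% statement is correct. The endpoint is descriptive (SAP 5.3) and has no margin, so no decision turns on it. The single readings remain available in Listing 26.

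All of that stands. It means that the pre-specified result should not be replaced. It does not supply limits for one reading.

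Four stronger readings are tempting, and the documents do not support them.
- A reader might infer that the planned limits miss their stated 95%. They do so only if tested against a pair that the SAP does not define.
- A reader might infer that the single-reading analysis was removed. SAP 8.2 records it as an unplanned repeat at one interim. It was never in the protocol, and no decision to drop it is recorded.
- A reader might infer that the mean-based limits are far too narrow, with coverage below 90%. That needs within-series SDs of about 2 mmHg or more, or a much smaller other-source SD, and the documents give neither.
- A reader might infer that first-replicate limits would show agreement in home use. Clinic readings are taken by site staff and home readings by patients (Protocol 8.4.4.15), so patient handling is not captured.

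Narrowing is also not certain. SAP 7.3 gives no variance formula and cites a method for repeated observations. If within-series variance were added back, the effect would vanish. No such step is stated, and the repeat with the first replicate suggests that there was none.

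**Conclusion.** The point holds as an inexpensive improvement to reporting; the planned limits are not in error. SAP 7.3 and 7.5.1 yield limits for a three-reading mean only, and the final plan offers none for a single reading.

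That single-reading limits would be wider rests on two conditions: within-series errors are at least partly independent, and no within-series variance is added back. On the scales in the protocol, the mean-based limits are about 2% to 7% narrower and cover about 94.5% to 93% of single-reading differences. Both inputs to that range are assumptions. Only the trial's own replicate readings can give the actual size.

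**What to change.** In SAP 7.3 and 7.5.1, and in the titles of Tables 25 and 26:
1. Keep the mean-based limits as the pre-specified result, and state that they apply to the mean of three consecutive ARGOS readings.
2. For V05 to V09 and for V10 to V11, add companion limits for a single clinic reading. Either use the first replicate, or add two thirds of the within-series ARGOS variance to the variance of the mean-based difference. State which method is used.
3. Report the within-series SD of the ARGOS readings.
4. Describe the companion limits as single clinic readings taken by site staff, not as home-use agreement.

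The three readings per series are already recorded, and the first-replicate analysis has been run once, so the extra work should be small. The downside is that the single-reading limits will be slightly wider than the main result. Listing them as a companion analysis leaves the pre-specified endpoint unchanged.
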